4.4 Lost to Follow-up Criteria

Patients in the PS or RPS cohort who fail to return within 13 months and cannot be contacted after at least two phone calls (each at least 24 hours apart) or other attempts via registered mail, courier, or email will be classified as lost to follow-up.

Exception: If patients notify investigators in advance of inability to attend a scheduled visit or examinations due to special reasons, this is not considered lost to follow-up. In such cases,

investigators should encourage patients to undergo examinations at other medical institutions and provide results through appropriate forms.

5 Sample Size Estimation

As an observational real-world study, sufficient sample size is needed to reflect real-world conditions and balance patient heterogeneity. Based on the number of participating centers and patient flow, approximately 33,000 patients are expected to be enrolled for analysis.

6 Study Procedures

6.1 Clinical Information to be Collected

6.1.1 The collection information and time point of PS Cohort

Starting from September 2020, outpatient or inpatient patients with CHB who meet inclusion criteria and have been screened through the exclusion criteria will be enrolled after informed consent. Baseline data and scheduled follow-up assessments will be collected at fixed time points after treatment initiation. Recommendations are based on the guidelines and clinical evidence. Actual schedules may be adjusted by treating physicians. No additional visits will be imposed by the study [2].

A recommended follow-up schedule and assessments are summarized in Table 1.

Table 1 Study visit table

	Baseline	V1	V2	V3	V4	V5	V6	V7	V8	V9	V10	V11	V12	V13
Study week	0	4±1	12±2	24±4	36±4	48±4	72±4	96±4	120±4	144±4	168±8	192±8	216±8	240±8
Time point	0	1m	3m	6m	9m	1y	1.5y	2y	2.5y	3y	3.5y	4y	4.5y	5y
Demographics	★													
Height & weight	★													
Medical history	★													
Family history	★													
Clinical assessment														
Symptoms and signs	★			★	★	★	★	★	★	★		★		★
Treatment regimen	★			★	★	★	★	★	★	★		★		★
Clinical events ^a	★	★	★	★	★	★	★	★	★	★	★	★	★	★
Laboratory tests														
Quantitative HBsAg	★	★	★	★	★	★	★	★	★	★	★	★	★	★
HBeAg, anti-HBe, anti-HBc, anti-HBs	★	★	★	★	★	★	★	★	★	★	★	★	★	★
HBV DNA	★	★	★	★	★	★	★	★	★	★	★	★	★	★
Complete blood count	★	★	★	★	★	★	★	★	★	★	★	★	★	★
Hepatic panel	★	★	★	★	★	★	★	★	★	★	★	★	★	★
Creatinine	★			★		★		★		★		★		★

AFP & CEA	★			★		★		★		★		★		★
INR & PT	★			★		★		★		★		★		★
TC, TG, HDL-c, LDL-c	★			★		★		★		★		★		★
Glucose	★			★		★		★		★		★		★
HbA1c														
Creatine kinase														
Electrolytes (K, P, Ca)														
Urinalysis														
Imaging^b and liver pathology														
Transient elastography	★			★		★		★		★		★		★
Abdominal ultrasound	★			★		★		★		★		★		★
Abdominal MRI														
Abdominal CT														
Liver biopsy														

a Clinical events include decompensated cirrhosis, HCC, death, or liver transplantation

b If abdominal ultrasound is unavailable, MRI or CT may be used as an alternative and will be treated as required completion items

c The study does not mandate MRI/CT/liver histology, but when these tests are performed in routine care, their results will be collected to enrich observational data

6.1.2 The collection information of RPS Cohort

6.1.2.1 Retrospective data collection

Clinical records from baseline up to the date of informed consent will be collected retrospectively, according to the study visit table (Table 1). Any items not performed in routine care will be recorded as missing data.

6.1.2.2 Prospective data collection

Subsequent visits will follow the windows specified in the study visit table (Table 1). The initial prospective visit will depend on the interval between baseline date and the consent date.

Example: If baseline was October 2020 and consent was signed in December 2023 (an interval of 3 years), prospective follow-up would begin at V9 (corresponding to 3 years).

6.1.3 The collection information of RS Cohort

Clinical data generated between September 2020 and the implementation of Protocol Version 3.0 will be retrospectively collected (items based on the study visit table, Table 1, with time points recorded according to when they actually occurred). Any items not collected in routine practice will be recorded as missing data.

6.2 Follow-up Management and Measure to Ensure Patient Compliance

The study aims to achieve a follow-up rate of more than 80%. As this is a non-interventional study, measures will be taken to maximize patient compliance. At both initial and follow-up visits, patients will receive education and reminders to attend subsequent scheduled follow-ups on time.

The study database system includes functions that regularly notify site investigators of recommended follow-up time points, prompting physicians to conduct visits and complete data collection and entry as needed. In addition, patient education booklets containing follow-up record forms will be distributed, encouraging patients to adhere to regular follow-up, consistently document their test results, and gain a better understanding of their disease status and treatment outcomes.

7 Study Termination Criteria

The study will be terminated if:

- 1) Major flaws or serious deviations occur during implementation, making evaluation infeasible.
- 2) Adverse events or serious adverse events related to treatment occur during the study, and investigators deem it unsafe to continue.
- 3) Regulatory authorities, government departments, or ethics committees request suspension

or termination of the study.

- 4) Other circumstances arise that investigators consider make continuation inappropriate or impractical.

8 Efficacy Evaluation

8.1 Effectiveness

8.1.1 Primary Objectives:

To compare the 5-year incidence of HCC under different treatment regimens.

8.1.2 Secondary Objectives:

- 1) Compare the 1-year, 2-year, 3-year, 4-year, and 5-year rate of HBsAg seroclearance and HBsAg seroconversion under different treatment regimens.
- 2) Compare the 5-year incidence of decompensated cirrhosis and its complications under different treatment regimens
- 3) Compare the 5-year incidence of cirrhosis under different treatment regimens
- 4) Compare proportion of patients with improvement or progression of liver fibrosis under different treatment regimens
- 5) Compare the 5-year incidence of liver transplantation under different treatment regimens
- 6) Compare the 1-year, 2-year, 3-year, 4-year, and 5-year HBsAg levels, the decline changes of HBsAg from baseline, the rate of HBeAg seroconversion, the decline changes of HBV DNA from baseline, and the proportion of HBV DNA undetectable (<20 IU/mL) under different treatment regimens
- 7) Compare the relapse rate after treatment cessation under different treatment regimens

8.1.3 Exploratory Objectives:

Describe the demographic characteristics of patients in the real-world clinical setting.

8.1.4 Methods for Assessing Efficacy Endpoints:

8.1.4.1 HCC: According to the 2019 National Health Commission diagnostic criteria for hepatocellular carcinoma, a diagnosis of HCC will be considered confirmed when either pathological or clinical criteria are met. Pathological confirmation requires diagnosis by two or more pathologists as hepatocellular carcinoma. Clinical diagnosis requires at least one typical imaging features about nodules and liver cancer on dynamic contrast-enhanced MRI, dynamic contrast-enhanced CT, contrast-enhanced ultrasound, or hepatocyte-specific contrast (Gd-EOB-DTPA) MRI; a diagnosis is established if either of the following is satisfied: 1) any nodule size ≥ 2 cm with one typical imaging feature; 2) all nodules sizes ≤ 2 cm with two typical imaging features. During follow-up, any HCC event must include recording of pathology reports (including

subtype, differentiation, and presence/distribution of intravascular tumor clusters) or imaging descriptions (including imaging modality that showed typical HCC features and nodule size), and scanned copies of original reports must be provided for centralized verification by the study team.

8.1.4.2 Decompensated cirrhosis: According to 2019 Chinese Society of Hepatology guidelines on the management of liver cirrhosis, a diagnosis of cirrhosis will be considered confirmed when either pathological or clinical criteria are met, and when clinical manifestations suggest decompensated will be considered to be decompensated cirrhosis [31]. Pathological confirmation requires diagnosis by two or more pathologists as decompensated cirrhosis. Clinical criteria require that endoscopic evidence of esophagogastric varices, ultrasound or CT findings suggesting cirrhosis or portal hypertension, or liver stiffness measurement [LSM] values reaching corresponding thresholds. Clinical features of decompensation include ascites, variceal hemorrhage, spontaneous bacterial peritonitis/sepsis, hepatic encephalopathy, or hepatorenal syndrome, confirmed by laboratory tests, imaging, or clinical scoring systems. On occurrence of decompensated cirrhosis during follow-up, investigators must document pathology (including number of pseudo-lobules, inflammation and fibrosis staging), or supporting ancillary test results (e.g., presence of varices, imaging features suggesting cirrhosis/portal hypertension, specific LSM values, ascites, variceal bleeding), and laboratory or clinical records indicating decompensation (e.g., temperature, cognitive assessment scales, inflammatory markers, blood ammonia, liver and renal function). Original reports and scans must be provided for verification by the study team.

8.1.4.3 Changes in HBsAg, HBeAg, and HBV DNA will be analyzed by comparing baseline and follow-up values.

8.2 Safety Objectives:

Observe the drug safety under different regimens

9 Adverse Event Recording

Adverse event (AE) is any unfavorable medical occurrence in a research participant, not necessarily having a causal relationship with the study. Serious adverse event (SAE) or reaction is any untoward medical occurrence that results in death, life-threatening, requiring or prolonging hospitalization, persistent or significant disability or incapacity, congenital anomaly or birth defect, or an important medical event in the investigator's judgment.

Expected AEs: As a observational real-world study that only collects clinical data and medical history without imposing additional procedures, visits, or costs, no extra risks are anticipated theoretically. However, obtaining consent and taking medical histories may cause psychological discomfort; investigators should therefore be careful with phrasing and patient communications.

Recording and management of AEs: If a patient experiences psychological discomfort during history taking, study staff should provide verbal reassurance and record the incident within 2 hours, notifying the designated study personnel. For patients showing persistent or severe psychological symptoms (e.g., depression, mania), psychiatric consultation and psychological support should be arranged within 12 hours, and the event recorded by designated personnel. For unexpected injuries or harms related to the study, appropriate treatment and compensation will be provided. All AEs observed during the study must be documented in detail. If SAEs occur, designated personnel will manage and record the event promptly and report to the ethics committee and relevant authorities within required timelines. Serious or unexpected adverse reactions not consistent with drug labeling will be reported to the hospital's pharmacovigilance/ADR monitoring department per relevant requirements.

10 Statistical Analysis Plan

Details of statistical methods and definitions of analysis datasets are provided in the separate Statistical Analysis Plan (SAP).

11 Data Management and Confidentiality

(1) Data Entry and Modification

Data entry and corrections are performed by investigators. All entered data must originate from source documents (e.g., original medical records, laboratory reports) and be consistent with original records. All observations and test results should be entered promptly, accurately, completely, clearly, and truthfully into case report forms and the electronic database. Data managers will review and manage entered data. For data queries, data managers will send queries to investigators, who should respond promptly; data managers may re-query if necessary.

(2) Confidentiality of Participant Information

All study participant information must be strictly confidential. Participant records and data will be identified by study ID numbers rather than names. Identifiable information will not be disclosed outside the study team without participant consent. All study staff are required to maintain confidentiality. Participant files will be stored in locked cabinets accessible only to authorized study personnel. To ensure regulatory compliance, government regulators or ethics committee members may inspect personal records at the study site per regulations. Any publications will not disclose participants' personal identifiers.

(3) Confidentiality of Study Data

Study data are confidential. Study staff must not disclose data to individuals outside the project without the principal investigator's authorization, nor transfer data to external institutions without hospital authorization. Transfer of human genetic resources or related data to foreign entities or domestic entities with foreign capital requires approval by the National Human Genetic Resources Administration; normal academic result publication that complies with regulations is permitted.

12 Quality Control and Assurance

The principal investigator will organize relevant training to ensure the study is conducted according to standards, and that case report forms and other documents comply with GCP principles and the protocol. All data and materials must be verifiable. Quality control will be applied at every study stage to ensure data reliability and correct execution of procedures. The principal investigator must ensure investigators adhere to the protocol, confirm data accuracy, and ensure completeness of reports and informed consent documentation prior to study initiation. Any protocol deviations should be reported to the ethics committee in a timely manner.

When necessary, the study team will develop standard operating procedures (SOPs) and implement quality control procedures throughout study conduct and data handling to ensure standardization and reliability.

13 Ethical Considerations

This observational study collects medical history and routine laboratory/imaging results and does not impose additional burden or costs on participants; therefore, it does not present additional theoretical risks. The study will be conducted after approval by the Huashan Hospital Ethics Committee and other relevant local ethics committees; participating sites must obtain approval from their own ethics committees prior to commencement. All eligible patients will sign informed consent forms. Participant information will be kept strictly confidential and recorded using study ID numbers rather than names. The study will be conducted in compliance with applicable national regulations (e.g., Measures for Ethical Review of Biomedical Research Involving Humans) and international ethical guidelines such as the Declaration of Helsinki. The Huashan Hospital Ethics Committee will perform continuing oversight of the study.

14 Recruitment and Informed Consent Process

Participants will be recruited from outpatient clinics and inpatient wards at participating centers when they are diagnosed with CHB. The study team will inform clinicians across relevant departments about recruitment criteria. Clinicians who identify eligible patients during routine

care will notify the study team. Study staff will then visit the patient, fully inform them of the study's risks and benefits, and obtain written informed consent.

15 Responsibilities of Participating Parties and Other Provisions

Responsibilities of lead site (Huashan Hospital):

1. Establish a standard operating procedure for the multicenter registry within the study, and define standards for each process (including enrollment criteria, database audit standards, and data statistical workflow); appoint database managers and quality control personnel to conduct regular checks on data entry quality and study progress at each site;
2. Coordinate data aggregation and analysis;
3. Assign personnel responsible for enrollment, follow-up, and data collection/recording at Huashan Hospital.

Sub-centers responsibilities:

Appoint personnel responsible for patient enrollment, follow-up, data collection, and record-keeping at each sub-center.

16 Reference

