This is an observational, multicenter, real-world study led by Huashan Hospital. Approximately 98 sub-centers are expected to participate. Randomization and blinding are not involved in this study. It will only observe and collect data related to the changes of clinical indicators during routine treatment. The physicians will make clinical decisions based on the applicable guidelines and evidence at the time of enrollment, combined with clinical experience and patient-specific conditions. No additional interventions will be imposed, and clinical decisions will not be influenced by this study.

The study consists of three cohorts (Figure 1):

Prospective cohort (PS cohort): Patients enrolled before the implementation of Protocol Version 3.0 who were planned or currently undergoing antiviral therapy. Clinical data will be prospectively collected for five years after informed consent has been obtained. The total follow-up period will last five years.

Retrospective-prospective cohort (RPS cohort): Patients received antiviral therapy whose initial clinical visit occurred before Protocol Version 3.0 but signed informed consent after its implementation. The study will retrospectively collect treatment and examination records from baseline (defined as the date patient first visited the study center for CHB starting from September 2020, with concurrent HBV DNA, liver function, and abdominal ultrasound results) and will prospectively collect subsequent clinical data up to five years from baseline. The total follow-up period will last five years.

Retrospective cohort (RS cohort): Patients receiving antiviral therapy whose clinical records from September 2020 until the implementation of Protocol Version 3.0 will be retrospectively collected.

[figure not shown]

Figure 1 Schematic diagram of the study design

Patients enrolled at sites before Version 3.0 are assigned to the PS cohort, those enrolled before Version 3.0 belong to the RS cohort, and whether to belong to the RPS cohort is depending on

patients' willingness. Patients at newly added sites after Version 3.0 are included in the RS cohort, and may, depending on patients' willingness, be included in the RPS cohort.

4 Eligibility Criteria, Exclusion Criteria, and Withdrawal Criteria

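### The protocol does not mask the study-team verifiers of HCC and decompensation to regimen, so acceptance of borderline events could depend on the regimen being compared

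*Protocol*

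**What the plan says.** - **Primary objective (Protocol 8.1.1):** "To compare the 5-year incidence of HCC under different treatment regimens". Decompensated cirrhosis by regimen is a secondary objective (8.1.2).
- **Masking (Protocol 3):** "Randomization and blinding are not involved in this study". This is the only statement on masking in the document.
- **HCC (Protocol 8.1.4.1):** HCC is confirmed either by two or more pathologists or by a clinical rule that combines nodule size with typical imaging features, for example "any nodule size ≥ 2 cm with one typical imaging feature". At follow-up, "any HCC event must include recording of pathology reports" or imaging descriptions, and "scanned copies of original reports must be provided for centralized verification by the study team".
- **Decompensation (Protocol 8.1.4.2):** cirrhosis is confirmed first, and then "when clinical manifestations suggest decompensated will be considered to be decompensated cirrhosis". The features are to be supported by laboratory tests, imaging or clinical scores. "Original reports and scans must be provided for verification by the study team".
- **Where regimen data sit:** treatment regimen is in the same visit table as the clinical events (Table 1). Under section 15 the lead site appoints the database managers and also has the task "Coordinate data aggregation and analysis".
- **What is deferred:** section 10 leaves statistical methods and the definitions of analysis datasets to the SAP. Who verifies events is settled in the protocol.

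**The concern.** The protocol sets up a central check on the endpoint that carries the main conclusion, gives it to the study team, and does not keep the regimen from the people who make the check. Some cases need judgement: whether an imaging feature is typical, how a nodule at the 2 cm boundary is handled (the two size rules both include 2 cm), and whether clinical signs suggest decompensation. The Background section also records an expectation about direction, namely lower HCC incidence with PegIFN than with NA monotherapy. A verifier who knew the regimen could apply a slightly different standard without meaning to.

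If that happened, outcome misclassification would differ by regimen. It would act directly on the regimen contrast. Adjustment for baseline confounders would not remove it, because it arises after baseline and in the outcome. It also does not shrink as patients are added, whereas the confidence interval does.

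Open, physician-chosen treatment is part of an observational study and is not criticised here. The point concerns only the verification step, which can be masked without touching care.

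**Working it through.** The protocol gives no acceptance rate, HCC risk or regimen share, so there is no figure to reproduce. The check has two parts.

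**1. The text.** Sections 8.1.4.1 and 8.1.4.2 name the verifier (the study team) and the material (reports and scans). Section 3 says there is no blinding. Section 11 identifies records by study ID instead of name, which hides the patient but not the regimen. No section provides a verifier outside the study team, removes regimen information from the packet, or requires a decision before linkage to treatment. Masking of verifiers is therefore not provided for. What the verifiers actually see is not stated.

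Exposure differs by endpoint:

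| Event type | Basis for acceptance | Room for judgement at verification |
|---|---|---|
| HCC, pathology | Two or more pathologists | Least |
| HCC, imaging | Nodule size and number of typical features, taken from reports | More |
| Decompensation (secondary) | Clinical manifestations, supported by tests or scores | Most |

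**2. Size.** Let *f* be the share of events that are borderline and *d* the extra proportion of those rejected in one regimen, with acceptance otherwise complete and true risks equal.

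Apparent ratio = 1 − *f* × *d*

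Assumed ranges: *f* = 10-30%, *d* = 2-10 percentage points.

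| *f* | *d* | *f* × *d* | Apparent ratio |
|---|---|---|---|
| 0.10 | 0.02 | 0.002 | 0.998 |
| 0.10 | 0.10 | 0.010 | 0.990 |
| 0.30 | 0.02 | 0.006 | 0.994 |
| 0.30 | 0.10 | 0.030 | 0.970 |

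To see what the worst of these does to a test, take the planned 33,000 patients in two equal groups of 16,500, a true 5-year HCC risk of 4% in both (assumption), and a two-sided 0.05 test of two proportions with pooled null variance.

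- Accepted risks: 0.0400 and 0.0400 × 0.97 = 0.0388, a difference of 0.0012.
- Pooled risk 0.0394; SE = √(0.0394 × 0.9606 × 2/16,500) = 0.00214.
- Shift = 0.0012 / 0.00214 = 0.56.
- False-positive rate = Φ(0.56 − 1.96) + Φ(−0.56 − 1.96) = 0.081 + 0.006, about 8.7% instead of 5%.

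With a 1% risk and the same ratio, the difference is 0.0003, the SE is √(0.00985 × 0.99015 × 2/16,500) = 0.00109, the shift is 0.28 and the rate is about 5.9%. At a ratio of 0.998 the rate stays at about 5.0% in both cases. With equal acceptance in the two regimens, which is what masking aims for, the ratio is 1.00 and the rate is 5.0%.

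**The case against.** **Nobody says the verifiers see the regimen.** This stands. A reader might infer that verification is done by people who know the treatment. The no-blinding sentence describes a non-interventional design, not the verification procedure, and the HCC packet listed in 8.1.4.1 does not include the regimen. The documents support only that masking is not provided for.

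**Verifiers check reports against written criteria.** This largely stands for HCC. The packet consists of reports; no re-reading of images is stated. Much of the judgement therefore lies with the site radiologist or pathologist. For decompensation the requirement of laboratory, imaging or scoring support narrows the room but does not close it.

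**The bias could be made to look much larger.** A reader might apply the rejection gap to all events and get ratios of 0.98-0.90 for gaps of 2-10 points. That is not justified when only borderline events are in doubt; the gap must be multiplied by the borderline share.

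**Masking here is neither the only safeguard nor a full one.** This stands. Masked image reading, masked pathology reading and masked analysis are also possible. Only events reported by sites reach verification, so regimen-dependent detection or reporting would remain.

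**It is operational detail.** Sections 12 and 15 allow for operating procedures that are not shown, and these might cover it. But the protocol itself names the verifier and the material, and it leaves only statistical matters to the SAP, so the safeguard belongs next to that text.

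**Conclusion.** The point holds as a cheap improvement to a stated procedure. The study team verifies HCC and decompensation, the study is declared unblinded, and nothing masks the verifiers to regimen, so acceptance of borderline events could depend on the regimen. This is a possibility. The documents do not show that bias occurs, in which direction, or that verifiers know the treatment.

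The size is modest: an apparent ratio of about 0.998-0.97 when the truth is 1.00. In the two-group illustration with equal groups and 1-4% risk, the false-positive rate is between about 5.0% and 8.7%. Every input except the planned 33,000 is an assumption, including complete acceptance of all other events. Pathology-confirmed HCC is least exposed and decompensation most.

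**What to change.** Add to Protocol 8.1.4.1 and 8.1.4.2 that the existing study-team verifiers:

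- see only the pathology, imaging, laboratory and clinical reports needed to apply the criteria, under study ID;
- have the regimen and cohort fields withheld, with drug names covered where they appear on the scans;
- record their decision before the event is linked to treatment data.

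No new readers, visits or changes to care are needed. The cost is a restricted database view and redaction of scans arriving from about 98 sub-centers, which is real work, mainly for decompensation packets that contain clinical records. Masking will be imperfect where laboratory results or notes reveal treatment; the Background section itself lists bone marrow suppression as an interferon effect. The change does not reach regimen-dependent detection or reporting at sites, and the protocol should not claim that it does.

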For example, retrospective analyses of previous studies show that although PegIFN plus NAs as initial combination therapy yields significantly higher HBsAg clearance rates than NA monotherapy, comparisons with PegIFN monotherapy yield inconsistent results. Sequential PegIFN therapy after NAs also improves HBsAg clearance compared with continued NA monotherapy, but few studies compare it directly with PegIFN monotherapy [12,13,17,20–27]. Improvements in fibrosis observed with PegIFN sequential therapy suggest additional benefit over NAs alone, but comparative data remain limited. Patients treated with PegIFN show a lower

incidence of HCC compared with NA monotherapy, but comparative data among PegIFN monotherapy, sequential therapy, and initial combination therapy are lacking. Regarding treatment duration, whether extending PegIFN therapy beyond the currently recommended 48 weeks provides additional benefit remains uncertain. Some studies report that extending therapy to 72 or 96 weeks in HBeAg-negative patients yields higher HBsAg clearance rates than 48 weeks, though without statistical significance due to small sample sizes [28,29]. Other studies indicate that extending sequential PegIFN therapy to 96 weeks after NA-induced HBeAg clearance does not significantly improve HBsAg clearance compared with 48 weeks [24].

Therefore, the advantages and disadvantages of different antiviral strategies for CHB—particularly their effects on long-term outcomes such as HCC and decompensated cirrhosis—remains insufficient. Large-scale, long-term, high-quality clinical studies are urgently needed to provide robust evidence for optimizing antiviral regimens.

This study aims to establish a nationwide, multicenter, real-world cohort to compare long-term outcomes under different treatment regimens. The goal is to generate high-quality evidence to guide treatment and follow-up of chronic viral hepatitis, support optimization of therapeutic strategies, and accelerate progress toward a functional cure.

2 Aims

To explore the long-term outcomes of antiviral therapy for CHB with the incidence of HCC as the primary endpoint, in order to identify optimal clinical decision-making strategies for the management of CHB.

3 Study design

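### Section 8.1.4.2 accepts ultrasound or CT but not MRI as imaging evidence of cirrhosis, although Table 1 lets MRI stand in for ultrasound, so MRI-only cases can go uncounted

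*Protocol*

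**What the plan says.** Section 8.1.4.2 works in two steps. Cirrhosis must first be confirmed by pathology or by clinical criteria, following a cited 2019 national guideline. Then, "when clinical manifestations suggest decompensated will be considered to be decompensated cirrhosis". The clinical criteria for the first step are endoscopic varices, "ultrasound or CT findings suggesting cirrhosis or portal hypertension, or liver stiffness measurement [LSM] values reaching corresponding thresholds". The second step needs a clinical event: "Clinical features of decompensation include ascites, variceal hemorrhage, spontaneous bacterial peritonitis/sepsis, hepatic encephalopathy, or hepatorenal syndrome".

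Section 8.1.4 has no separate assessment paragraph for cirrhosis without decompensation. The first step of 8.1.4.2 is therefore the only definition the protocol offers for secondary objective 3 (5-year incidence of cirrhosis), as well as the entry condition for secondary objective 2 (decompensated cirrhosis and its complications).

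Table 1 (section 6.1.1) treats imaging differently. Footnote b reads: "If abdominal ultrasound is unavailable, MRI or CT may be used as an alternative and will be treated as required completion items". The last footnote says that MRI, CT and histology are not mandated, but that "when these tests are performed in routine care, their results will be collected to enrich observational data".

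**The concern.** The visit table and the endpoint definition do not accept the same imaging. A site can meet the Table 1 imaging requirement with an MRI, see cirrhosis on it, and still hold nothing that the imaging criterion of 8.1.4.2 recognises. If no other route is met, the case drops out of objective 3. If a complication such as ascites follows, it also drops out of objective 2, because the first step was never satisfied.

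There is a second, practical risk. With about 98 sub-centers expected, some will read the list literally and others will take it to cover any cross-sectional imaging. The same patient could then be an event at one center and not at another.

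**Working it through.** The plan states no figure on this point to reproduce. The check is a comparison of the passages, followed by an illustration of size on assumed shares.

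**Step 1: the modality lists side by side**

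| Place | Purpose | Ultrasound | CT | MRI |
|---|---|---|---|---|
| Table 1, footnote b | completing the visit's imaging | yes | yes, as substitute | yes, as substitute |
| Table 1, last footnote | collecting routine results | – | yes | yes |
| 8.1.4.1 | HCC, clinical diagnosis | yes (contrast-enhanced) | yes | yes (two kinds) |
| 8.1.4.2 | cirrhosis, imaging criterion | yes | yes | **not named** |

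Only 8.1.4.2 leaves MRI out. The HCC definition just before it lists modalities one by one and names MRI twice, so the shorter list cannot safely be taken as shorthand for all imaging.

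**Step 2: who is lost**

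Under the literal criteria, a true cirrhosis case is missed only if all of these hold:

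1. MRI shows cirrhosis, and no ultrasound or CT shows it;
2. there is no endoscopic evidence of varices;
3. there is no qualifying pathology;
4. there is no stiffness value at threshold.

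A decompensation with variceal bleeding seen at endoscopy meets the varices route anyway. For objective 2 the gap therefore concerns mainly ascites, peritonitis/sepsis, encephalopathy and hepatorenal syndrome.

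**Step 3: does elastography close the gap?**

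Table 1 stars transient elastography at baseline, V3, V5, V7, V9, V11 and V13, which are the visits starred for abdominal ultrasound. Often, then, a stiffness value will exist. It is not guaranteed. Section 6.1.1 calls the schedule recommended and lets physicians adjust it, and sections 6.1.2.1 and 6.1.3 record items not done in routine care as missing for the retrospectively collected data.

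**Step 4: illustrative size**

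Share of true cases missed = m × q, where

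- m = share of true cirrhosis cases whose imaging is MRI only (assumed 2%, 5%, 10%);
- q = share of those with no qualifying stiffness value, endoscopy or pathology (assumed 10%, 30%, 50%).

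| m | q = 10% | q = 30% | q = 50% |
|---|---|---|---|
| 2% | 0.2% | 0.6% | 1.0% |
| 5% | 0.5% | 1.5% | 2.5% |
| 10% | 1.0% | 3.0% | 5.0% |

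Per 1,000 true cases this is 0.002 × 1,000 = 2 at the low end and 0.05 × 1,000 = 50 at the high end. Neither m nor q is in the protocol.

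**The case against.** The best defence is that the gap is narrow and perhaps only verbal. Three arguments support it.

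- **Documentation wording.** When decompensation occurs, 8.1.4.2 asks sites to record evidence such as "imaging features suggesting cirrhosis/portal hypertension, specific LSM values, ascites, variceal bleeding", with no modality named, and adds that "Original reports and scans must be provided for verification by the study team". A sensible verifier would accept an MRI. But this sentence says what to file once an event has been declared; it does not widen the criteria for declaring one. It also applies to decompensation, not to cirrhosis alone, so it gives no help for objective 3.
- **Purpose of footnote b.** It concerns completeness of visits, not endpoint definition. That is true, but it is also why the two need to agree: the footnote allows visits at which the only image is one that the definition ignores.
- **Other routes.** Elastography is planned at the same visits, and endoscopy or pathology also qualify. This stands and is the reason the effect is small. An MRI done in addition to an ultrasound that itself shows cirrhosis loses nothing.

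A reader might go further and infer that cirrhosis is also overcounted, because the criteria are joined by *or* and one stiffness reading during treatment would seem enough. The protocol does not establish this. It refers to thresholds that correspond to something, under a guideline that is not at hand, and its silence on repeats or timing does not show that no conditions apply. Nor does it support a bias that differs by regimen: it says nothing on how stiffness or ALT behaves under either drug class, and it does not say that fibrosis change is measured by elastography.

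**Conclusion.** The mismatch is real on the text and minor in effect. Read literally, cirrhosis evidenced only by MRI is not counted, and decompensation in such a patient is not counted either. The error runs in one direction, an undercount, and touches secondary objectives 2 and 3 only. Its size is unknown; 0.2–5% of true cases is an illustration that rests wholly on assumed shares. If the same fraction were missed under every regimen, incidences would fall slightly and their ratios would not change. The protocol gives nothing from which to judge whether MRI use differs by regimen.

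It would be wrong to read this as decompensation being miscounted in both directions. A falsely high stiffness value cannot create a decompensation event by itself, because a confirmed clinical feature is also required.

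**What to change.** In the clinical criteria of 8.1.4.2, extend the imaging item from two modalities to three (ultrasound, CT or MRI), so that it agrees with footnote b of Table 1. Apply the amended wording to all three cohorts, including records already collected. If leaving MRI out was intended, the section should say so.

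The cost is one word in a protocol amendment and a note to sites. MRI results are already gathered under the Table 1 footnotes, so no visit, test or data field is added. MRI-only cases entered so far would need to be looked at again.

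A compulsory confirmation rule for stiffness-based cirrhosis, by repeat reading or by ALT, is not part of this fix. Elastography is starred at weeks 24, 48, 96, 144, 192 and 240. From week 48 on, the next reading is 48 weeks away (96 − 48 = 48), and a first qualifying value at week 240 could never be confirmed by a later scheduled one. That is a trade-off for the sponsor to weigh, not a correction that the documents call for.
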